6.3.1.1.1 Seizure Type Identification

Characteristics of the seizure types to be observed and recorded for efficacy assessments (i.e., subject/caregiver diaries) include:

- Tonic: body stiffening, upward deviation of the eyes, pupil dilation, and altered respiratory patterns
- Atonic: brief loss of muscle tone and consciousness, that may result in an abrupt fall
- Myoclonic: sudden muscle jerks and including infantile spasms
- Tonic-clonic: jerking preceded by stiffening
- Clonic: repeated jerking
- Absence: lapses of awareness, sometimes with staring
- Febrile: seizure of various types (especially tonic-clonic) associated with high fever
- Focal: typically involving 1 side and/or region of the body, twitching, and grimacing
- Atypical absence: staring (as in an absence seizure), but subject may also be somewhat responsive.

These observable characteristics will be utilized to assist the parents(s)/caregiver(s) and subject (if applicable) in categorizing seizures types in the subject seizure and dosing diary. The Investigator will fully train the parents(s)/caregiver(s) and subject (if applicable) in methods to identify seizure type.

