8.0 STATISTICS

8.1 Determination of Sample Size

The sample size will be determined by the number of subjects who are eligible to and elect to rollover from INS011-14-029 or INS011-15-054. These studies would contribute up to a maximum of 60 and 20 subjects respectively.

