8.3.6.1 Seizure-related Data

All seizure-related parameters (in terms of raw data and percentage change from baseline) will be listed and summarized by dose and for all subjects using descriptive statistics (mean, number, SD, median, minimum, and maximum values for continuous variables).

No statistical inferential procedures will be performed.

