2.2. SECONDARY OBJECTIVES

The secondary objectives are:

- To establish the continued efficacy of Cannabidiol Oral Solution in maintaining seizure control in subjects with treatment-resistant seizures that previously completed INS011-14-029 or Part A (Visit 6) in INS011-15-054.
- To assess the global status of subjects taking Cannabidiol Oral Solution for an extended period of time determined by various qualitative assessments.
- To monitor for changes in plasma levels of cannabidiol and its 7-OH metabolite during long-term treatment of subjects with treatment-resistant seizure disorders, including LGS, DS and IS.

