6.5. STATISTICAL TESTS

No statistical inferential procedures will be performed for this study.

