16.2.1.1. Seizures-Related Variable(s) & Derivation(s)

The following variables will be used to assess the control of seizures:

- Type of seizures:
 - Tonic: body stiffening, upward deviation of the eyes, pupil dilation, and altered respiratory patterns
 - Atonic: brief loss of muscle tone and consciousness, that may result in an abrupt fall
 - Myoclonic: sudden muscle jerks and including infantile spasms
 - Tonic-clonic: jerking preceded by stiffening
 - Clonic: repeated jerking
 - Absence: lapses of awareness, sometimes with staring
 - Febrile: seizure of various types (especially tonic-clonic) associated with high fever
 - Focal: typically involving 1 side and/or region of the body, twitching, and grimacing
 - Atypical absence: staring (as in an absence seizure), but subject may also be somewhat responsive.
- Seizure frequency:

For tonic and atonic seizures, the number of seizures will be recorded. For other types of seizures, the frequency will be reported by range as follows:

- None
- 1 to 5 seizures
- 6 to 19 seizures
- 20 to 50 seizures

Document: C:\Users\q832483\Documents\Insys CSR\Pending\Ready for QC\New folder\Statistical Analysis Plan.docx
Author: [REDACTED] Version Number: V1.0 Final
Version Date: 04APR2017

Template No: CS_TP_BS016 – Revision 3
Effective Date: 01May2012

Reference: CS_WI_BS005

[REDACTED]

- > 50 seizures.
- Seizure severity:

The assessment of seizure severity will be recorded by the parent(s)/caregiver(s) in the subject seizure and dosing diary. Seizure severity will be categorized as:

- Mild
- Moderate
- Severe

Overall seizure severity will be captured using the CGI-S as described in [Section 16.2.2](#).

- Seizure duration:

The approximate timing of seizure will be recorded by the parent(s)/caregiver(s) in the subject seizure and dosing diary.

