16.2.1.3. Analysis of Seizures-Related Variable(s)

Seizure-related parameters will be summarized as follows:

- Number of subjects (and corresponding percentage) that experienced, by maximum severity, a tonic and atonic seizure, per time point and age category.
- Descriptive statistics (n, mean, SD, median, minimum, and maximum) of the actual number and duration of tonic and atonic seizures, by time point and age category.
- Descriptive statistics (n, mean, SD, median, minimum, and maximum) of the change from baseline in the number and duration of tonic and atonic seizures, by time point and age category.
- Number of subjects by maximum severity, maximum number of seizures and seizure duration for each other types of seizures by time point and age category.
- For each tonic and atonic seizure type, figures will display:
 - Number of seizures per subjects over time by age category
 - Average number of seizures over time by age category and by modal dose category, where modal doses will be clustered as follows:]0;10],]10;20],]20;30],]30;40].

Supportive listings will also be performed for tonic and atonic seizures, and for other types of seizures separately. The listings will include all the related data recorded in the *Subject Diary – Seizure Record* eCRF page.

Document: C:\Users\q832483\Documents\Insy CSR\Pending\Ready for QC\New folder\Statistical Analysis Plan.docx
Author: [REDACTED] Version Number: V1.0 Final
Version Date: 04APR2017

Template No: CS_TP_BS016 – Revision 3
Effective Date: 01May2012

Reference: CS_WI_BS005

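### For the seven seizure types other than tonic and atonic, including infantile spasms and the main Dravet types, the SAP plans no change or shift from baseline and does not declare this departure from the protocol

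*SAP*

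**What the plan says.** The efficacy objective in SAP 2.2 is "To establish the continued efficacy of Cannabidiol Oral Solution in maintaining seizure control in subjects with treatment-resistant seizures". It is not limited to particular seizure types.

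Protocol 8.3.6.1 states the analysis broadly: "All seizure-related parameters (in terms of raw data and percentage change from baseline", it says, will be listed and summarised with descriptive statistics. SAP 16.2 says that frequency, duration and severity will be compared with each baseline, and SAP 16.2.1 names the previous-study baseline as the comparator. Neither restricts this by seizure type.

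SAP 16.2.1.1 lists nine seizure types. Tonic and atonic seizures are counted. "For other types of seizures, the frequency will be reported by range as follows": none, 1-5, 6-19, 20-50, >50. Infantile spasms fall in this second group, because both documents class them with myoclonic seizures (protocol 6.3.1.1.1: "Myoclonic: sudden muscle jerks and including infantile spasms").

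SAP 16.2.1.3 then plans descriptive statistics for "change from baseline in the number and duration of tonic and atonic seizures". For each other type it plans the number of subjects by maximum severity, maximum number and duration at each time point and by age category, plus listings. The figures of seizures over time are also confined to tonic and atonic.

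SAP 3.3, which records changes from the protocol, mentions only that the by-dose presentation is dropped.

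**The concern.** The detailed analysis section delivers less than the protocol, and less than the SAP's own introduction to the efficacy outcomes. The types left out are not marginal: they include infantile spasms and nearly every type that the protocol gives for Dravet syndrome. Tonic and atonic seizures are core types for Lennox-Gastaut syndrome (protocol 1.2.1), so the change analysis suits that syndrome better than the other two that the study names.

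At stake is whether the seizure-control objective can be answered within subject for these types. Maintained control is a statement about the same subject over time. Counts per category at each visit do not show who improved, who stayed the same and who got worse. They can also shift only because the contributing subjects change: withdrawn subjects are not replaced (protocol 3.4.3), and missing values are not imputed (SAP 7.2 and 16.2.1.2).

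**Working it through.** No power or error-rate figure is involved. The SAP states that "No statistical inferential procedures will be performed for this study". The check compares sections, with a little counting.

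**1. Types with a baseline-referenced analysis.** The nine types in SAP 16.2.1.1 are tonic, atonic, myoclonic (with infantile spasms), tonic-clonic, clonic, absence, febrile, focal and atypical absence. SAP 16.2.1.3 gives change from baseline for two. 9 − 2 = 7 have none.

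**2. Dravet types.** Protocol 1.2.2 lists six: generalized clonic, generalized tonic-clonic, atypical absence, myoclonic, focal, and tonic, which it marks as rare. Atonic is not listed. Only tonic is in the change analysis, so 6 − 1 = 5 are outside it.

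**3. Promise against plan.**

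| Source | Seizure types covered | Comparison with baseline |
|---|---|---|
| Protocol 8.3.6.1 | All | Percentage change |
| SAP 16.2, 16.2.1 | Not restricted | Compared with baseline |
| SAP 16.2.1.3 | Tonic, atonic | Change in number and duration |
| SAP 16.2.1.3 | Other seven | None named |
| SAP 3.3 | n/a | Narrowing not listed |

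Protocol 8.2.1 lets methods change without an amendment, but requires the SAP to document the change. This one is not documented.

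**4. Why per-visit counts do not substitute.** Suppose *a* of *n* subjects are in a high-frequency category, and *d* of those *a* then leave while nobody else changes. The proportion moves from a/n to (a − d)/(n − d), which is smaller whenever a < n. The table would show improvement although no subject improved. A shift table restricted to subjects with both values does not have this artefact.

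**5. How much a shift table of ranges can show.** The largest fall that stays inside one range is (upper − lower)/upper:
- 20-50: (50 − 20)/50 = 60%
- 6-19: (19 − 6)/19 = 68%
- 1-5: (5 − 1)/5 = 80%
- >50: no upper limit, so no bound

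The ranges are coarse, and a shift table will miss some real change.

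**6. Subjects affected.** Protocol 8.1 gives only rollover maxima by source study: "These studies would contribute up to a maximum of 60 and 20 subjects respectively". No split by syndrome and no seizure types per subject are given, so the number cannot be computed.

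**The case against.** **The protocol promise is narrower than it looks.** Section 8.3.6.1 ties its statistics to continuous variables, and a percentage change cannot be calculated from a range such as 6-19. Limiting numeric change in frequency to the counted types therefore follows from how the data are recorded. This stands for percentage change in frequency, but it does not remove the gap. Duration is timed in the diary and could be compared with baseline for any type. Protocol 6.3.1 treats ranges as a fallback where exact recording is not possible, whereas the SAP makes them the rule. Ordinal data also allow a shift table, which SAP 16.2.2.3 already uses for CGI-S.

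**Other measures cover every subject.** SAP 16.2.1.1 assigns overall seizure severity to CGI-S, and 16.2.2.3 plans CGI-S shift and change from both baselines whatever the seizure type. This stands, and it means that seizure control is partly assessed. But CGI-S is a global severity rating and does not measure frequency or duration by type.

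**Baseline may be one of the time points.** SAP 16.2.1.3 does not say, and the table templates are not available. Even if baseline were a column, the counts as described would be marginal and would not pair each subject with his or her own baseline.

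**The consequence is small.** Protocol 6.3.4 and SAP 16.2 say that efficacy data are not endpoints. The study is uncontrolled and background antiepileptic drugs may be changed. This stands and limits the weight of the point. Continued seizure control is nevertheless a stated objective, and the data will be reported.

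**Conclusion.** The point holds as an undeclared narrowing of the analysis. Seven of nine seizure types, including infantile spasms and five of the six Dravet types listed in the protocol, have no planned within-subject comparison of frequency or duration with baseline. This conflicts with protocol 8.3.6.1 and with SAP 16.2 and 16.2.1. It affects the secondary objective on seizure control and no safety conclusion. It should be corrected before database lock.

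A reader might infer more than the documents support:
- *That seizure control cannot be assessed for these types.* Category counts, listings and CGI-S shifts remain.
- *That most Dravet or infantile-spasms subjects are affected.* The protocol's remark that tonic seizures are rare in Dravet syndrome is disease background and not enrolment data. Classing spasms as myoclonic does not show that those subjects have no tonic or atonic seizures.
- *That the INS011-15-054 rollovers are the infantile-spasms group, so that a share of the 80 could be quoted.* The documents do not say so, and 20 and 80 are both maxima.
- *That the efficacy objective is defined by the three syndromes.* It refers to treatment-resistant seizures. The syndromes are named in the safety and plasma-level objectives.

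The conclusion assumes that SAP 16.2.1.3 is followed as written and that the templates add no baseline comparison.

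**What to change.** In SAP 16.2.1.3, for each seizure type other than tonic and atonic, add:
- a shift table of the maximum daily frequency range (none, 1-5, 6-19, 20-50, >50) from the previous-study baseline to Week 24, Week 36 and Final Visit, with n (%) improved, same or worse among subjects with both values;
- the same table for maximum severity;
- change from baseline in duration, where duration was recorded.

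Using the maximum keeps to the summary that the SAP already plans. The SAP should state that the ranges are per day, as protocol 6.3.1 has them. In SAP 3.3, record that shift replaces percentage change for types recorded by range.

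Seizure-free days by type are not a workable addition. The daily diary question described in SAP 16.2.1.2 asks about any seizure, and the documents do not show that it was asked at the previous-study baseline.

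The cost is SAP wording and a few tables. Previous-study seizure data are already needed for the tonic and atonic analysis. There are two limits: the ranges are coarse (a fall from 50 to 20 per day, 60%, stays in one category), and the tables depend on the previous-study baseline diary having used compatible categories, which should be confirmed first.

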6.3 Efficacy

6.3.1 Seizure Control

In this study, seizure frequency, duration, and severity will be assessed to monitor seizure control achieved by long-term treatment with Cannabidiol Oral Solution. Seizures will be observed and recorded using a patient reported outcome (PRO) instrument (i.e.,

subject/caregiver diaries). The exact format and version(s) of diary to be used will also be included in the eCRF. Diaries will be dispensed at Visits 7, 8, and 9 (Weeks 12, 24, and 36) and reviewed and completed pages collected (if applicable) during each visit.

For the purposes of this study, only observable seizures will be quantified in the one week prior to Visits 8, 9, and 10. All seizures should be recorded by the parent(s)/caregiver(s) and/or subject (if applicable) in the diary.

Given that continuous seizures may be observed in some subjects (i.e., multiple seizures may occur without break), it may not be possible to accurately record all seizures for these subjects. If necessary, the parent(s)/caregiver(s) or subject (if applicable) will, at a minimum, categorize the seizure frequency (for seizures others than tonic or atonic seizures) by range (i.e., diaries will record the count of seizures per day as >50 seizures/day, 20 to 50 seizures/day, 6 to 19 seizures/day, 1 to 5 seizures/day, or no seizures).

The subject and/or his/her parent(s)/caregiver(s) are responsible for completing the diary. The party who is primarily responsible will be chosen by the Investigator in consultation with the subject's parent(s)/caregiver(s). If a pediatric subject will be entering diary data, the parent(s)/caregiver(s) should provide guidance and monitor accuracy and completeness.

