16.2.1.2. Missing Data Methods for Seizures-Related Variable(s)

All data will be evaluated as observed; no imputation method for missing values will be used.

The eCRF includes the following question on each study day: "Did the subject experience any seizures?". If the response to this question is no, it will be assumed that the subject does not have any seizures on that day. If the question is not answered, it will be not assumed that the subject does not have any seizures that day (i.e., it will be assumed that the question is inadvertently not answered).

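### For seven of nine seizure types the only clearly specified frequency summary is the worst diary day, which hides changes in the number of bad days when these are frequent and at least one remains

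*SAP*

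**What the plan says.** SAP 16.2.1.1 lists nine seizure types and treats them in two ways. Two types are counted: "For tonic and atonic seizures, the number of seizures will be recorded". The remaining seven are only banded: "For other types of seizures, the frequency will be reported by range as follows". There are five bands, from none through 1–5, 6–19 and 20–50 up to more than 50, and the SAP list gives no time unit. Protocol 6.3.1 supplies it: "diaries will record the count of seizures per day as >50 seizures/day, 20 to 50 seizures/day", and so on down to none.

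The diary covers one week per time point (Protocol 6.3.1: "only observable seizures will be quantified in the one week prior to Visits 8, 9, and 10"), and recording is daily (SAP 16.2.1.2: "The eCRF includes the following question on each study day"). A day on which that question is unanswered is not taken as seizure-free.

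SAP 16.2.1.3 then plans descriptive statistics of the actual values, of the "change from baseline in the number and duration of tonic and atonic seizures, by time point and age category", and figures, all for tonic and atonic seizures only. For the rest it plans "Number of subjects by maximum severity, maximum number of seizures and seizure duration for each other types of seizures by time point and age category". Their daily records go into listings.

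Protocol 8.3.6.1 was broader: "All seizure-related parameters (in terms of raw data and percentage change from baseline) will be listed and summarized by dose and for all subjects". SAP 16.2 also says that seizure frequency will be compared with each baseline. SAP 3.3 declares one departure from the protocol, the replacement of by-dose displays by age category. It does not mention dropping a change summary for seven seizure types.

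**The concern.** The seven types are myoclonic (which includes infantile spasms), tonic-clonic, clonic, absence, febrile, focal and atypical absence. Infantile spasms are one of the three conditions named in the objectives, and continued seizure control is a stated secondary objective in SAP 2.2.

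A maximum over days ignores how many days were bad. Once one bad day is present, further bad days add nothing, and removing all but one takes nothing away. It also tends to rise with the number of days over which it is taken, so subjects with more answered days tend to have higher maxima at the same underlying frequency. If many children have frequent bad days, a real gain or loss of control for these types could be missing from the tables and visible only by reading listings.

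**Working it through.** **Plan's own figure.** None. The documents give no expected frequency, sample size or precision for this summary, so there is nothing to reproduce. The daily chances below are assumptions and are shown over a range.

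**Inputs from the documents.** Nine listed types minus tonic and atonic = 7 types (SAP 16.2.1.1). Ranges are per day (Protocol 6.3.1). There are up to 7 diary days per time point (Protocol 6.3.1). The summary is the maximum (SAP 16.2.1.3).

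**Single child.** Call a day bad if it falls at or above a chosen range, for example 6 or more seizures. The weekly maximum is bad if at least one of the 7 days is bad. A fall from 7 bad days to 1 is a change of (1 − 7)/7 = −86%. If the remaining bad day is in the same range as before, the maximum does not change. The same holds for a rise from 1 to 7.

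**Group, independent days.** With daily chance p of a bad day, the share of subjects with a bad maximum is 1 − (1 − p)^7.

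| p before → after | Fall in bad days | Share before | Share after |
|---|---|---|---|
| 0.9 → 0.3 | 67% | 1 − 0.1^7 = 100.0% | 1 − 0.7^7 = 91.8% |
| 0.8 → 0.4 | 50% | 1 − 0.2^7 = 100.0% | 1 − 0.6^7 = 97.2% |
| 0.3 → 0.1 | 67% | 1 − 0.7^7 = 91.8% | 1 − 0.9^7 = 52.2% |
| 0.15 → 0.05 | 67% | 1 − 0.85^7 = 67.9% | 1 − 0.95^7 = 30.2% |

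The same 67% fall therefore shows as about 8, 40 or 38 percentage points, depending on where p starts.

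**Correlated days.** With beta-binomial days (within-subject correlation 0.1 to 0.5), halving the bad days lowers the share by 2–4% in relative terms from 6 expected bad days per week, 11–12% from 4, 19–26% from 2 and 23–35% from 1. The pattern does not rest on independence.

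**All five ranges.** With Poisson daily counts, going from 10 to 5 per day leaves 97.6% and then 96.6% of subjects with a maximum in the 6–19 range. Going from 4 to 2 per day moves that share from 81.6% to 11.0%. The maximum is blind within a range and responds when a cut-point is crossed.

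**Number of days contributing.** At one expected bad day per week (p = 1/7), the share with a bad maximum is 1 − (6/7)^7 = 66% with 7 days, 1 − (6/7)^4 = 46% with 4 and 1 − (6/7)^3 = 37% with 3. Unanswered days can produce such differences, and so can the windows in SAP 6.4. Week 24 takes seizure records dated Days 158 to 178, while Visit 8 may fall 10 days either side of Day 168. A visit on Day 161 has diary Days 154 to 160, of which only Days 158 to 160 lie in the window.

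**Comparison.** The expected percentage of answered days that are bad is p itself. It would show 90% to 30% in full, and its expectation does not depend on the number of days answered if those days are representative.

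**The case against.** The strongest reply is that the saturated examples are a selected case. The table bears this out: from low or moderate daily chances the maximum moves by about 40 points, and the documents do not say where the seven types lie. A reader might infer that any large gain or loss of control would appear as no change, in either direction. The documents do not support that. A rise from 1 to 3 expected bad days per week moves the share from 66% to 98%, cut-point crossings show, and a maximum of none shows that the type was not recorded on the answered days.

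A reader might also infer that the daily ranges are thrown away. They are not: SAP 16.2.1.3 lists them. They are only left unsummarised.

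The worst-day reading is itself inferred. The SAP does not define the maximum, Protocol 6.3.1 offers daily ranges as a minimum for subjects whose seizures cannot all be counted, and the output templates cited in SAP 8 are not available here. SAP 13 also plans a bar chart of mean seizure number by number of antiepileptic drugs. Its wording is ambiguous but most naturally covers tonic and atonic only, and no scoring rule is given for averaging ranges. These points justify saying clearly specified rather than simply only.

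Finally, efficacy data are not endpoints (Protocol 6.3.4, SAP 16.2), no inference is planned, the CGI scales and IPES are summarised, and marked worsening or a new seizure type is reportable as an adverse event (Protocol 6.1.1). This lowers the priority. It does not fill the gap, since none of these measures how often these seizure types occur.

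**Conclusion.** The point holds with limits. For seven of nine seizure types, the only clearly specified frequency summary is the weekly worst-day range. It conceals changes in the number of bad days when these are frequent and at least one remains: nothing shows for a child going from seven to one, and about 8 points show for a group in which bad days fall by two thirds from a daily chance of 0.9. When bad days are few it responds well. Which case applies to which type cannot be settled from the documents. The maximum also depends on how many diary days contribute, so unequal diary completion or windowing can move it without any change in seizures.

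The conclusion rests on reading the maximum as the worst day and on the assumed daily chances. The group percentages also assume independent days, though the correlated-day results show the same pattern. Because the data are descriptive and not endpoints, this is a moderate-priority improvement, not a flaw that invalidates the seizure analysis.

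**What to change.** In SAP 16.2.1.3, for each of the seven types, summarise per subject and time point:

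- the percentage of answered diary days in each of the five ranges;
- the number of days free of that type per 7 answered days;
- the change from baseline in both, where baseline diary data allow.

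Keep the maximum as a supportive row, and state that it is the highest daily range among the answered days at that time point. Do not use the median daily range instead: over 7 days it stays bad from 7 bad days down to 4 and not bad from 3 down to 0, so it too hides large changes.

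The cost is SAP wording, a small derivation and some extra table rows. The data are already on the Subject Diary – Seizure Record eCRF page, so nothing new has to be collected.
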